5.5.2 Cigarette Use

The average number of cigarettes used by each subject from familiarization V2 to V3 will be calculated, in addition the average from baseline (V3) to the following visits will be calculated, these visits include V4, V14 (Month 1), V28 (Month 2), V43 (Month 3) which corresponds to cigarettes smoked from baseline to acute effect visit, end of Month 1, end of Month 2 and end of Month 3 respectively.

5.5.3 IQOS Use

The average number of IQOS Heat sticks used by each subject from familiarization V2 to V3 will be calculated, in addition the average IQOS use from baseline (V3) to the following visits will be calculated, these visits include V4, V14 (Month 1), V28 (Month 2), V43 (Month 3) which corresponds to Heat sticks used from baseline to acute effect visit, end of Month 1, end of Month 2 and end of Month 3 respectively.

6 SAMPLE SIZE JUSTIFICATION

The sample size of 20 per arm (smoking abstinence with training, IQOS with training, continued cigarette smoking with training) was determined based on previously published results, which reported a standard deviation of 14 mL/kg/min in VO₂max in the change

Confidentiality Statement

Philip Morris Products SA.	Statistical Analysis Plan	Confidential
P1-EXC-01-EU	Final 2.0	Page 30 of 71
Related to PMI-RRP-WKI-112487		SAD DI EYC OI EU

between groups which continued smoking and those who were smoking abstinent after participating in a 12-week training program (Albrecht, et al. 1998). This sample size allows a probability of 90% that the half-width of the 95% confidence intervals between two arms have a precision of approximately 10.3 mL/kg/min.

For example, if the mean difference in change between the cigarette arm and smoking abstinence arm was 12 mL/kg/min after training, we expect that if the experiment were repeated many times then on average 90% of the time the 95% confidence intervals of the mean differences between two arms will be within 1.7 and 22.3. To allow for a dropout rate of approximately 20%, the sample size will be 25 per arm. The IQOS-2 arm without training will mainly serve as a secondary analysis to the IQOS-1 arm with training, and the drop-out rate in this arm is expected to be lower. Therefore, only 15 subjects will be randomized to this arm.

CHANGES FROM THE PROTOCOL SPECIFIED STATISTICAL 7 ANALYSES

An exploratory analysis of VO2max and exercise capacity will be carried out on subjects with additional biochemical verification of smoking status.

8 **ANALYSIS SETS**

The main population for non-safety analysis will be the As Exposed Exercise Compliant Set. Safety will be analyzed using the Safety Set.

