## **Statistical Methods:**

## Sample Size and Evaluation:

The sample size of 20 per arm (smoking abstinence with training, *IQOS* with training, continued cigarette smoking with training) was determined based on previously published

Data and information contained in this document are considered to constitute trade secrets and confidential commercial information, and the legal protections provided to such trade secrets and confidential information are hereby claimed under the provisions of applicable law. No part of this document may be publicly disclosed without the written consent of Philip Morris Products S.A

Philip Morris Products SA	Clinical Study Protocol	Confidential
P1-EXC-01-EU	Version 3.0 / 2 May 2019	Page 14 of 151

results, which reported a standard deviation of 14 mL/kg/min in VO2max in the change between groups which continued smoking and those who were smoking abstinent after participating in a 12-week training program (2). This sample size allows a probability (power) of 90% that the half-width of the 95% confidence intervals between two arms have a precision of approximately 10.3 mL/kg/min. For example, if the mean difference in change between the cigarette arm and smoking abstinence arm was 12 mL/kg/min after training, we expect that if the experiment were repeated many times then on average 90% of the time the 95% confidence intervals of the mean differences between two arms will be within 1.7 and 22.3. To allow for a dropout rate of approximately 20%, the sample size will be 25 per arm. The *IQOS*-2 arm without training will mainly serve as a secondary analysis to the *IQOS*-1 arm with training, and the drop-out rate in this arm is expected to be lower. Therefore, only 15 subjects will be randomized to this arm.

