3.3 Study Hypotheses and Evaluation Criteria

3.3.1 Hypotheses

This study is descriptive and therefore no statistical hypothesis will be tested.

Confidentiality Statement

PMI RESEARCH & DEVELOPMENT

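### The sample-size example says 90% of the 95% confidence intervals would lie within 1.7 to 22.3; with 20 per arm, SD 14 and a true difference of 12, about 25% do

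*SAP*

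**What the plan says.** SAP 6 bases the size on the three trained arms: "The sample size of 20 per arm (smoking abstinence with training, IQOS with training, continued cigarette smoking with training"). The variability comes from a published 12-week training study, "which reported a standard deviation of 14 mL/kg/min" for the change in VO2max. Two statements follow.

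- **Width.** The design gives a "probability of 90% that the half-width of the 95% confidence intervals between two arms have a precision of approximately 10.3" mL/kg/min.
- **Worked example.** Taking a mean difference of 12 mL/kg/min between the cigarette and abstinence arms, the text continues "we expect that if the experiment were repeated many times then on average 90% of the time" and completes the claim with: "on average 90% of the time the 95% confidence intervals of the mean differences between two arms will be within 1.7 and 22.3".

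The 20 per arm is then raised to 25 for about 20% dropout. Protocol 12.2 and the Sample Size and Evaluation paragraph of the synopsis carry the same example. SAP 3.3.1 states: "This study is descriptive and therefore no statistical hypothesis will be tested".

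**The concern.** The limits 1.7 and 22.3 are 12 − 10.3 and 12 + 10.3. The example takes the 90% that belongs to the half-width and attaches it to the position of the whole interval. A CI stays inside the band only if it is narrow enough and its centre is close enough to 12. The first condition has about 90% probability. The second is ignored, although the centre is an estimate that varies from repeat to repeat.

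Because no hypothesis is tested, expected precision is the only stated reason for the size of the study, and the example is the part that tells a reader what the cigarette-versus-abstinence interval should look like. Taken at its word, it says that with a true difference of 12 the lower limit would be at least 1.7 in at least 90% of repeats. The documents also expect the variability estimates to help size later studies, so a wrong precision statement could be carried forward.

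**Working it through.** **Inputs (SAP 6).** n = 20 evaluable per arm; SD = 14 mL/kg/min, taken as the common per-arm SD of change; two-sided 95% CI; difference Δ = 12; band 1.7 to 22.3, that is 12 ± 10.3; dropout 20%. The interval is the unadjusted pooled two-sample t interval, df = 2 × 20 − 2 = 38.

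**Step 1: reproduce the plan's width statement.**

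- SE of the difference = 14 × √(2/20) = 4.427
- t(0.975, 38) = 2.0244, so the half-width when the estimated SD equals 14 is 2.0244 × 4.427 = 8.962
- Half-width not exceeded with 90% probability = 8.962 × √(χ²(0.90, 38)/38) = 10.23
- Pr(half-width ≤ 10.3) = Pr(χ²₃₈ ≤ 38 × (10.3/8.962)²) = 0.911

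Conditioning on the interval covering the true difference gives 10.25 and 0.908. Either way the stated 10.3 and 90% reproduce, which also confirms that 14 is used as the per-arm SD. The dropout step reproduces too: 20/(1 − 0.20) = 25.

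**Step 2: the example.** With half-width H and estimated difference d, the CI lies inside the band only if |d − 12| + H ≤ 10.3. At H = 8.962 the slack is 10.3 − 8.962 = 1.338, or 1.338/4.427 = 0.302 SE. Integrating over the distribution of the pooled variance:

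Pr(CI within 1.7 to 22.3) = E[2Φ((10.3 − H)/SE) − 1], taken over H ≤ 10.3, = **0.2495**

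Simulation agrees: 0.250 drawing from the sampling distributions (2,000,000 draws) and 0.251 from 200,000 raw-data trials.

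**Step 3: where the intervals fall.**

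| Quantity (n = 20 per arm, SD 14, Δ = 12) | Value |
|---|---|
| CI wholly within 1.7 to 22.3, as stated in the plan | 90% |
| CI wholly within 1.7 to 22.3, recomputed | 25.0% |
| Lower limit below 1.7 | 37.9% |
| Upper limit above 22.3 | 37.9% |
| Both | 0.8% |
| CI within the band, given half-width ≤ 10.3 (0.2495/0.9109) | 27.4% |
| Band centred on 12 that holds 90% of CIs | 12 ± 16.4, or −4.4 to 28.4 |

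Check: 100 − (37.9 + 37.9 − 0.8) = 25.0.

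**Step 4: does any other reading give 90%?**

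| Reading | Result |
|---|---|
| SD treated as known (z interval) | 29% |
| 14 is the SD of a difference between two subjects (per-arm SD 14/√2 = 9.90) | 79%, but the 90% half-width becomes 7.2 and the stated 10.3 no longer reproduces |
| Point estimate alone within 1.7 to 22.3 | 98% |
| All 25 per arm evaluable | 44% |
| 48 per arm | 89.2% |
| 49 per arm | 90.0% |

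None of the readings available at the planned size gives 90%.

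**The case against.** The strongest reply is that 12 is meant as the observed difference. The example directly follows the width statement and may only restate it loosely: if 12 were observed, the CI would be no wider than 1.7 to 22.3 about 90% of the time, and that is correct (91.1%). But the sentence refers to repeating the experiment many times, and the observed difference will not be 12 in every repeat. If this was the intended meaning, the text needs to say so. The reading makes the slip easier to understand and does not make the sentence true.

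A second reply is that nothing depends on the example. That stands. The correct width statement is one sentence earlier, the sample size is unaffected, and no model, estimate or decision rule uses the 1.7 to 22.3 band.

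A third is that 25% depends on exactly 20 evaluable per arm and unadjusted intervals, whereas SAP 9.6.1.1.1 plans a covariate-adjusted mixed model with arms defined by actual exposure. That also stands as a limit on use: 25% tests the sentence under its own inputs and does not forecast the precision of the reported results.

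**Conclusion.** The concern holds as stated. The example claims a 90% repeated-sampling property, and the design as described gives about 25%. The cause is a statement about interval width used as one about interval location, with the sampling error of the estimated difference left out. The figure assumes 20 evaluable per arm, a common per-arm SD of 14, a true difference of 12, normal data and unadjusted two-sample t intervals. These are the assumptions that reproduce the plan's own 10.3. Having all 25 randomized per arm evaluable raises it only to 44%. The error is confined to the example; the half-width of 10.3, the 20 per arm and the 25 per arm are arithmetically right.

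**What to change.** In SAP 6, delete the example or replace it with wording such as: *With 20 per arm and SD 14 mL/kg/min there is about 90% probability that the 95% CI half-width is at most 10.3 mL/kg/min; for an observed difference of 12, the CI would then be 1.7 to 22.3 or narrower with about 90% probability.* Make the same correction in Protocol 12.2 and the synopsis.

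The cost is wording in three places, with no change to sample size or analysis. Under Protocol 1.1 amendments go to the ethics committee, so the protocol text can be corrected at the next amendment. If none is planned, correct the SAP and note the point in the clinical study report.

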8.1 Full Analysis Set

The Full Analysis Set (FAS) consists of all randomized subjects who have at least one postrandomization product (cigarette or IQOS) use experience if randomized to IQOS, IQOS-2 or cigarette arm, and who have at least one valid non-safety assessment after randomization. All subjects in the SA arm who fulfil these requirements, except the product use experience, are part of this set as well. The FAS will be analyzed by randomized study arm.

8.2 Safety Set

The Safety Set consists of all subjects enrolled with signed ICF who have at least one valid safety assessment during the course of the study. The Safety Set will be analyzed by actual exposure (product use exposure, actual study arm).

Confidentiality Statement

Philip Morris Products SA.	Statistical Analysis Plan	Confidential
P1-EXC-01-EU	Final 2.0	Page 31 of 71
Related to PMI-RRP-WKI-112487		SAD DI EVC OI EU

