### 6.3.4 Stopping rules for Investigational Product

For safety purposes, use of the IP should be temporarily reduced or stopped in the event of any signs suggesting nicotine overexposure, e.g., gastrointestinal disturbance (nausea, vomiting, diarrhea, stomach, or abdominal pain), cold sweats, headache, dizziness, and breathing problems or any reasons at the discretion of the Investigator.

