5.5.1 Product Use Pattern

Actual product use pattern categorization is described in Figure 2 below,

Confidentiality Statement

Figure 2: Product Use Categorization

Note: HS: HeatSticks

The calculation of product use categories will be performed based on Figure 2. For each subject we will calculate product use for two time periods, representing Week 1 use and average product consumption from V3 till end of Month 3 or last visit prior to early termination whichever comes first.

- From V3 to V4: Week 1
- From V3 to V43/Last visit before early termination: Overall average consumption

For each time period the daily product use reported by a subject in the study will be summed up and averaged by the actual number of days the subject was in the study after randomization until date of last reported product use within the respective time period. This will then be multiplied by 30 to describe the average monthly product use.

For subjects who early terminated from the study, product use for overall average consumption will be calculated until the last visit prior to V44. For example, if a subject early terminated at V23 and subsequently came for V44, then product use will be calculated from V3 until the date of V23.

As both electronic diaries and paper diaries were used in the study concurrently for some subjects, the following rules will be applied in case of inconsistencies.

Confidentiality Statement

Philip Morris Products SA.	Statistical Analysis Plan	Confidential
P1-EXC-01-EU	Final 2.0	Page 29 of 71
Related to PMI-RRP-WKI-112487		SAP_P1-EXC-01-EU

- When there is data available for both electronic and paper diaries for the same date, the electronic diary data will be kept if both are the same. If the data is different on the same date, then data for this date will be considered missing.
- If a subject reports no product use but a value is recorded, we will assume that the number of product used reported was correct and use it in the derivation of product use.

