9.1.1 Stratified Presentation

Stratification criteria for the evaluation are:

- Randomized study arm Cigarette, IQOS-1, smoking abstinence (SA), IQOS-2) randomized arm.
- Product use (actual arm) i.e. actual product use exposure categorized based on self-reporting and biochemical verification according to Section 5.5.1 "Product Use Pattern":

Confidentiality Statement

Data and information contained in this document are considered to constitute trade secrets and confidential commercial information, and the legal protections provided to such trade secrets and confidential information are hereby claimed under the provisions of applicable law. No part of this document may be publicly disclosed without the written consent of Philip Morris Products S.A

Philip Morris Products SA.	Statistical Analysis Plan	Confidential
P1-EXC-01-EU	Final 2.0	Page 34 of 71
Related to PMI-RRP-WKI-112487		SAP_P1-EXC-01-EU

- o Cigarette,
- o IQOS-1,
- Smoking Abstinence (SA),
- IQOS-2,
- Dual users considered for IQOS-1 (Dual-1),
- Dual users considered for IQOS-2 (Dual-2),
- Cigarette consumption at V1 (10 to 19 cigarettes, more than 19 cigarettes per day)
- Sex (male, female)
- Age (<50, ≥ 50 years i.e. $21 \le Age < 50$ and $50 \le Age \le 65$])

The main stratification criterion for the evaluation is the actual product exposure, whereas data will be listed by randomization arm.

Further stratification by cigarette consumption and sex will be done for the analysis of VO_2max and exercise capacity and where explicitly defined. Further stratification by age and BMI will be done only where explicitly defined (e.g. for demographic data).

The AEECS, AEBECS and the Safety Set will be analyzed by actual study arm (product use exposure). The FAS will be analyzed by randomized study arm.

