Table 15.2.3.1.1: Overview of Adverse Events – Safety Set	X
Table 15.2.3.1.2: Summary of Adverse Events by System Organ Class and	
Preferred Term – Safety Set	X
Table 15.2.3.1.3: Summary of Adverse Events Related to Investigational	
Product and Expectedness, System Organ Class and Preferred Term - Safety Set	X
Table 15.2.3.1.4: Summary of Adverse Events by Severity, System Organ Class	
and Preferred Term - Safety Set	

Confidentiality Statement

Philip Morris Products SA.	Statistical Analysis Plan	Confidential
P1-EXC-01-EU	Pending Approval 0.1, CURRENT, IN PROGRESS	Page 69 of 71
Related to PMI-RRP-WKI-112487		DD SME01 810208 SAD D1

Table 15.2.3.1.5: Summary of Adverse Events Leading to Product	X
Discontinuation, Interruption or Reduction by System Organ Class and Preferred Term – Safety Set	X
Table 15.2.3.1.6: Summary of Adverse Events Leading to Study Discontinuation	X
by System Organ Class and Preferred Term – Safety Set	X
Table 15.2.3.1.7: Summary of Serious Adverse Events by System Organ Class	
and Preferred Term – Safety Set	
Table 15.2.3.1.8: Summary of Adverse Events related to Study Procedure by	
System Organ Class and Preferred Term – Safety Set	
Table 15.2.3.1.9: Summary of Frequent Adverse Events (Incidence >5%) by	
System Organ Class and Preferred Term – Safety Set	
Table 15.2.3.1.11: Summary of Device Events and Malfunctions - Safety Set	Х
Table 15.2.3.1.12: Summary of Medical History by System Organ Class and	
Preferred Term – Safety Set	
Table 15.2.3.1.13: Concomitant Medications by ATC and Preferred Drug Name	x
– Safety Set	^
Table 15.2.3.1.14: Concomitant Diseases by System Organ Class and Preferred	
Term – Safety Set	
Table 15.2.3.1.15: Prior Medications by ATC and Preferred Drug Name – Safety	x
Set	~
Table 15.2.3.2.1: Summary of Hematology Parameters by Product Use	
Category – Safety Set	
Table 15.2.3.2.2: Summary of Clinical Chemistry Parameters by Product Use	
Category – Safety Set	
Table 15.2.3.2.3: Summary of Urinalysis Parameters by Product Use Category –	
Safety Set	
Table 15.2.3.4.1: Summary of Vital Signs by Product Use Category – Safety Set	X
Table 15.2.3.4.2: Descriptive Statistics of ECG – Safety Set	X
Table 15.2.3.4.3: Descriptive Statistics of Spirometry at Screening, Discharge or	x
Early Termination – Safety Set	
Table 15.2.3.4.4: Summary of Physical Examination – Safety Set	X
Table 15.2.3.4.5: Summary of Cough-VAS and Likert Scales – Safety Set	Х

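### Adverse-event and device-event tables group subjects by post-randomisation product use over an unstated window, so an event that leads a subject back to cigarettes can leave the IQOS column

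*SAP*

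**What the plan says.** SAP 8.2 sets the grouping for safety: "The Safety Set will be analyzed by actual exposure (product use exposure, actual study arm". SAP 9.1.1 repeats it: "The AEECS, AEBECS and the Safety Set will be analyzed by actual study arm (product use exposure". Only the Full Analysis Set is analysed by randomised arm, and the planned table list (SAP 13.2) has no adverse-event table on that set.

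SAP 5.5.1 derives product use from the diary over two windows: "From V3 to V4: Week 1" and "From V3 to V43/Last visit before early termination: Overall average consumption". Daily use is summed and divided by days in the study. Then: "This will then be multiplied by 30 to describe the average monthly product use". Categories are read from Figure 2. For early terminators, "product use for overall average consumption will be calculated until the last visit prior to V44".

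SAP 9.6.4.1 and 9.6.4.2 count adverse events and device events within each study arm and in total. Neither section names a window or attributes an event to the product in use at onset. All the adverse-event tables (15.2.3.1.1 to 15.2.3.1.9) and the device-event table (15.2.3.1.11) use the Safety Set. Table 15.2.3.1.5 covers events leading to product "Discontinuation, Interruption or Reduction by System Organ Class and Preferred Term".

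Protocol 6.3.4 says "use of the IP should be temporarily reduced or stopped in the event of any signs suggesting nicotine overexposure". Under Protocol 5.2 and 6.3.2.1, an IQOS subject who uses other tobacco products is not discontinued for that.

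**The concern.** The grouping variable is measured after randomisation and can be changed by the event being counted. A subject with an early intolerance may stop IQOS, smoke again and remain in the study. The average then mostly reflects use after the event, and the event goes with the subject to whichever column the average dictates.

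This could affect how three tables read:

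- **Table 15.2.3.1.5.** The event that qualifies a subject for this table may also lead to a change of column.
- **Table 15.2.3.1.3 (relatedness).** Protocol 8.2.4 defines investigational product as cigarette or IQOS. An IQOS-related event in a reclassified subject would therefore appear as product-related under Cigarette or Dual.
- **Table 15.2.3.1.11 (device events).** An IQOS malfunction could be counted under Cigarette.

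The columns are small. The IQOS arms have 25 and 15 randomised subjects, so one subject is 1/25 = 4.0% or 1/15 = 6.7% of an arm as randomised.

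**Working it through.** The plan gives no figure to reproduce, so the check traces the rule and then applies its averaging formula.

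**Which window applies to safety?** SAP 9.6.4 names none. SAP 9.6.1.2 refers all other endpoints to Overall use, but that sentence is in the non-safety section and concerns baselines. Adverse events are collected from consent to end of study, and Overall is the only study-long window, so it is the natural reading. It remains an inference.

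**Inputs for the Overall window.** V43 is 106 ± 2 days after V3 (SAP 4.1). Assume h HeatSticks a day until day d, then h cigarettes a day to day 106.

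- HeatSticks per month = 30 × h × d/106
- Cigarettes per month = 30 × h × (106 − d)/106
- HeatStick share = d/106, whatever the value of h

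| Switch day d | HeatStick share | HeatSticks/month (h = 15) | Cigarettes/month (h = 15) |
|---|---|---|---|
| 7 | 6.6% | 29.7 | 420.3 |
| 14 | 13.2% | 59.4 | 390.6 |
| 30 | 28.3% | 127.4 | 322.6 |
| 53 | 50.0% | 225.0 | 225.0 |
| 90 | 84.9% | 382.1 | 67.9 |

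**Cut-offs.** Figure 2 is not shown, so the following are assumptions given as a range.

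- If IQOS requires a HeatStick share of at least c, the switch must be no earlier than day 106 × c: 53.0 for c = 50%, 74.2 for 70%, 95.4 for 90%, 100.7 for 95%. With a window of 104 or 108 days, the 50% point is day 52 or 54 and the 90% point is day 93.6 or 97.2.
- If Cigarette requires a cigarette share of at least c, a switch up to day 106 × (1 − c) puts the subject there: 10.6 for c = 90%, 31.8 for 70%, 53.0 for 50%.
- If IQOS allowed at most 5 cigarettes a month (the ceiling SAP 8.4 gives for smoking abstinence, borrowed here), the total allowed over 106 days is 5/30 × 106 = 17.7 cigarettes. That is about one to two days at 10 to 20 a day.

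**Early terminators.** Take IQOS to day 30, then the same daily number of cigarettes until a last visit k days later. The share is 30/(30 + k): 100% for k = 0, 90.9% for k = 3, 81.1% for k = 7. Such a subject may well stay in IQOS.

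***Others*.** SAP 5.5.1 puts a subject with more than 50% of diary data unavailable into *Others*, and SAP 9.4 says that group is listed but not analysed. SAP 9.6.1.2 does include *Others* in a second set of descriptive tables, but only for non-safety endpoints. Adverse events in these subjects may therefore be missing from the safety columns.

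**The case against.** Analysis by actual exposure is pre-specified in Protocol 12.4.3 and is a common choice for safety. The study is descriptive, with no hypothesis test. Data are listed by randomised arm (SAP 9.1.1), an adverse-event listing is planned, and relatedness is assessed event by event, so a misplaced event can be traced. The protocol's stopping rule speaks of a temporary reduction or stop and does not mention a return to cigarettes. A pause without cigarettes leaves the product mix unchanged. The labels Dual-1 and Dual-2 in SAP 9.1.1 also suggest that dual users stay identified with an IQOS arm.

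Much of this stands and limits the claim. Three stronger readings are not supported:

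- **That the SAP assigns adverse events by the V3–V43 average.** It names no window for safety.
- **That Table 15.2.3.1.5 necessarily loses its own subjects from the IQOS column.** It includes interruptions and reductions, which need not reclassify anyone. A discontinuation would do so only with enough later cigarette use.
- **That the bias runs one way, in favour of IQOS.** Cigarettes are also investigational product (Protocol 8.2.4), so the stopping rule covers them, and subjects willing to quit are encouraged to do so (Protocol 7.2). A cigarette-arm subject who stops after an event can leave that column too.

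What the objection does not answer is that a listing does not correct column counts or percentages, and no planned summary is free of behaviour after the event.

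**Conclusion.** The concern holds in a conditional form. The adverse-event and device-event tables rest on a post-randomisation grouping whose averaging window is not stated for safety. If the window is Overall, an early event followed by lasting cigarette use in a subject who stays in the study can be counted under Dual or Cigarette. Under an assumed requirement of a 50% HeatStick share, any such switch before day 53 leaves IQOS; under 90%, any before about day 95. These figures assume equal daily use, a single permanent switch and complete diaries.

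If Week 1 is meant, events after V4 cannot alter the grouping, but the label would then describe only the first week of a 106-day exposure. The SAP needs to say which applies.

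The number of subjects affected and the net direction cannot be determined from the documents. Adding tables by randomised arm is worthwhile without that number, because it removes the dependence on behaviour after the event.

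**What to change.** In SAP 9.6.4.1 and 9.6.4.2:

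1. State the window that defines the actual arm for safety, and how *Others* appear in the safety tables.
2. Add Tables 15.2.3.1.1 to 15.2.3.1.9 and Table 15.2.3.1.11 by randomised arm for all randomised subjects, beside the actual-use versions.
3. For Table 15.2.3.1.5, also show the product in use at adverse-event onset, taken from the diary, as counts or as a listing column. Counts or a listing avoid the need for exposure-time denominators.

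Randomised arm, adverse-event start dates and daily diary entries are already collected. The cost is SAP wording, a second run of existing table programs, and one derived variable for the third item.
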